Objective 4 (OUTCOMES): Improve and sustain **case management** of PPH and newborn resuscitation during observations of care, as measured by a) percent of women with undelivered placenta after 30 minutes who are

treated with oxytocin, and b) percent PPH cases that receive repeated dose of oxytocin or misoprostol, c) percent of newborns not breathing at birth who are breathing or being ventilated with bag & mask at one minute.

Objective 5 (IMPACT): Reduce over time: a) the percent of facility-based deliveries who experience PPH; b) the PPH-related case fatality rate, and c) the perinatal death rate (the fresh stillbirth rate and early newborn mortality rate at 24 hours or prior to discharge)¹.

Prior to presenting the hypotheses, we describe briefly below the three study arms and three time points of data collection. More description is provided in the Study Procedures section. (See Figure 1, page 11)

Table 1. Brief Description of Three Study Arms/Groups

Arm	Short Name	Component 1	Component 2	Component 3
		Training onsite (BAB, HBB) of providers, simulators left at facility	Peer Practice Coordinator (PPC) is trained and expected to hold weekly onsite practice sessions with providers	Mobile messages remind all trained providers to practice scenarios; and PPC has weekly mobile support from district trainer
1	Training-only	Yes	No	No
2	Partial Package	Yes	Yes	No
3	Full Package	Yes	Yes	Yes

Hypotheses

Overall Hypothesis: The partial package intervention (one-time, onsite training of providers, combined with low-dose, high-frequency peer-led practice sessions) and the full-package intervention (adding reminders and mobile support) will lead to significant gains in provider competencies (between immediately post-intervention to midline) and provider performance of key interventions *BAB* and *in HBB*, which are both maintained once the active intervention ceases.

Specific Hypotheses:

In BAB and in HBB related to the primary outcomes (see Section 4b5):

1. Provider competencies and performance will not decline (i.e. will be non-inferior) between midline and endline in the *full* package group.
2. Provider competencies and performance will not decline (i.e. will be non-inferior) between midline and endline in the *partial* package group.
3. At endline, the provider competency level and the performance level of the *partial* package group will be significantly higher than those of the training-only group.

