The study is a quasi-experimental design with three study arms/groups that receive different levels or intensities and modalities of the program intervention. Figure 1 (page 10) provides an overview of the intervention and evaluation components of the study. Briefly, the same simulator-based training will be provided in all three study arms. After the training, a simulator will be left in the health facility, and providers will be encouraged to practice with it regularly. In two of the study arms, specific health workers will be recruited to support the intervention by encouraging their colleagues to practice with the simulator. In one study arm, the practice will be further reinforced through mobile phone-based support. Following is a more detailed description of each of the three components.

Component 1 (Training): Training is composed of two separate training interventions. First, in each study facility, we will conduct a single day, simulator-driven training on PPH prevention and treatment; all providers who attend births will be invited to participate. Eight weeks later, in each facility, we will conduct a one-day, simulator-driven training for prevention and management of asphyxia in the newborn. After each one-day training, simulators will be left at the facility for practice with a corresponding practice schedule.

Component 2 (Peer-led Practice Sessions): On the day the first training (for PPH), 2 birth attendants at the facility will be selected to serve as peer practice coordinators (PPC). The PPCs will be trained to encourage their coworkers to participate in 15-minute practice sessions each week for 8 weeks, in which they will use the simulators to practice the skills learned in the one-day training. After the newborn asphyxia training occurs, these same PPCs will be trained to support a similar practice schedule for the following 12 weeks - 8 weeks for newborn asphyxia practice and 4 weeks for combined PPH and asphyxia skills practice.

Component 3 (Mobile phone-based support): (Note: This component is being negotiated with the ministry of health in conjunction with UNICEF due to the moratorium on mHealth interventions) Labor ward providers will be given mobile text messages for:

- 1) Content reminders
- 2) Practice reminders

[figure not shown]
PPCs will be connected to the district trainer via mobile phone for weekly phone calls during the practice periods to provide reminders and support for practice.

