5	Supplemental monthly summary report	This aggregated monthly form collects facility-level indicators related to this study, such as the number of women diagnosed with postpartum hemorrhage and the proportion of those women treated with oxytocin or misoprostol.
6	Participant Characteristics – Baseline	This self-administered questionnaire collects information about qualifications of training participants and their prior experience and confidence related to preventing and treating postpartum hemorrhage and neonatal asphyxia.
7	Knowledge Test: Bleeding	15 multiple choice questions that test providers' knowledge of the

Tool #	Title	Content
	after Birth	content taught in the Bleeding After Birth training.
8a-c	Observed Structured Clinical Examinations (OSCEs): Bleeding After Birth	Structured checklists that trainers will use to examine providers' skills related to routine care for third stage labor, retained placenta, and severe hemorrhage due to atony. Providers will demonstrate skills on a simulator.
9	Peer Practice Coordinators' Practice Log	In two of the study arms, peer practice coordinators will use this form to record when the providers at their facility practice with the simulator and the topic that they practice.
10	Phone Support for Peer Practice Coordinators	This will log the data and content of the weekly phone support that trainers have with peer practice coordinators (in one study arm only.)
11	Opt-in Sheet for Mobile Phone Reminders for Providers and PPCs	In one study arm, providers will have the option of receiving reminders about training content via their personal mobile phones.
12	Knowledge Test: Helping Babies Breathe	17 multiple choice questions related to the content taught in the Helping Babies Breathe training.
13 a, b	OSCEs: Helping Babies Breathe	Structured checklists that trainers will use to examine providers' skills related to neonatal resuscitation using stimulation and ventilation equipment. Providers will demonstrate skills on a simulator.
	Qualitative	
14	Focus group discussion guide	Health care providers will be asked about their experiences with the program, particularly what the factors that motivated or discouraged them from practicing with the simulator.
15	Semi-structured interview guide: Health facility in-charges	Health facility in-charges will be asked about their experiences implementing the program and for their opinions about how to strengthen and sustain it.

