2. Provider competencies and performance will not decline (i.e. will be non-inferior) between midline and endline in the *partial* package group.
3. At endline, the provider competency level and the performance level of the *partial* package group will be significantly higher than those of the training-only group.
4. At endline, the provider competency level and the performance level of the *full* package group will be significantly higher than those of the training-only group.

Hypotheses 1 and 2:

This is a non-inferiority analysis. Two-sided 90% confidence intervals (CI) for the difference in average knowledge and competence scores between midline and endline will be constructed, separately for full and partial package groups. Non-inferiority will be determined comparing the upper bound of the 90%CI for the difference between the 2 time points to the pre-specified non-inferiority margin of 0.06 (22). If the CI's upper bound is less than the predefined margin, then we are able to claim non-inferiority of the endline knowledge scores to the midline knowledge at a 0.05 level of significance.

We will first examine the differences in sample means of knowledge scores between midline and endline not adjusted for any potential confounding variables. The confidence intervals for the knowledge scores will be calculated using generalized linear models with knowledge and competencies as the dependent variables and time variable (endline vs. midline) as the primary independent variables. To account for repeated observations within providers at midline vs. endline, we will use robust Huber/White estimate of variance implemented in STATA through 'vce' (cluster) option. In addition, adjusted 90% CI for the difference in means will be constructed by adding provider- and facility-level factors in the model.

Hypotheses 3 and 4:

We will examine differences in competencies and performance at endline between the 3 study groups using generalized linear models. The dependent variables in these models will be:

- 1) knowledge and competency scores,
- 2) proportion of women who received **oxytocin** (at correct dosage) within one minute of a vaginal birth,
- 3) proportion of women whose placenta was inspected within 16 minutes, and
- 4) proportion of newborn checked for breathing within 1 minute.

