We will conduct a doer/non-doer analysis that will contrast providers and managers at facilities that adhere to low-dose/high-frequency practice recommendations with providers at facilities with few or no reported practice sessions. We will also analyze interviews with key stakeholders to identify their recommendations regarding program sustainability. Audio-recordings of focus group discussion and interviews will be transcribed and entered into Atlas.ti software. Data from close-ended questions will be entered into Microsoft Excel or Stata. Pre-determined and emergent codes will be developed, and content analysis will be conducted.

- 6) If human biospecimens (blood, urine, saliva, etc.) will be collected . N/A
- 7) Describe how **subjects** will be **screened for eligibility and assigned to** study/intervention and comparison/control groups.

All providers who attend births at the facilities will be invited to participate. All women who are in labor at the facility on the days of observation will be invited to participate (delivery and newborn care will be observed).

Criteria for being a PPC include: being an experienced skilled birth attendant and likely to remain at the facility during the study period (i.e. no imminent transfers).

- 8) Explain and justify whether there will be **blinding**.

Randomization or blinding of individual subjects is not feasible in this study because of the district-randomized design.

- 9) Explain and justify whether participants **will not receive routine care** or will have current therapy stopped.

Women in labor and delivery (participants) and their newborns will receive routine care as per Ugandan guidelines.

- 10) Explain and justify the use of a placebo or **non-treatment group**.

All study groups will receive the training on Bleeding after Birth and Helping Babies Breathe, and simulators (anatomic models) will be left behind at all facilities. The training-only (comparison) group will be encouraged to practice regularly but will receive no peer support intervention or SMS messages.

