Social, legal or economic	There is a risk to providers of possible loss of confidentiality of knowledge, test scores, and practice sessions and observation data on the performance of quality of care.	
The observers and study team will clearly explain the purpose of the assessment to the district authorities and facility-in-charges and obtain their approval for entering the facilities. The observers will explain the purpose of the assessment to providers and women, and obtain informed consent from providers and women in labor. Observers will be external to the facility. They will answer any questions. In addition, it will be explained to them that their observer is a trained maternity care provider. Observers will be as unobtrusive as possible. A strategy for keeping data confidential will be developed, followed and explained.
 
Information on the providers' performance on assessments or during direct observation of care will not be shared with their supervisors. Provider names will not be recorded on the data collection forms for assessments or observations and their identities will be kept separate from their data.
 
Providers' practice sessions with fellow providers will be logged using their names so PPCs can easily see who has practiced in a given week and whom they need to invite to practice. This log will be kept in a folder in the simulator case and will not be left out for casual review. In addition, supervisors will be told that provider refusal to participate in the study or practice sessions should in no way impact provider employment.
 
To ensure that the observations will not affect provider's employment, we will only provide aggregate data to facility supervisors and District staff. We will keep single-provider performance information confidential. We will develop a data flow and confidentiality plan.
 
Results for individual facilities may be reported to the MOH if requested, but reports for external dissemination will not present data at a level lower than a district.
 
There is no social, legal or economic risk to women.

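### Table 7 has trainers score the OSCEs, with no masking or independence required, so the endline between-arm comparison of OSCE competency can be biased by scorer leniency

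*Combined protocol and SAP*

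**What the plan says.** **Who scores.** Table 7 describes the HBB OSCEs (Tools 13a,b) as "Structured checklists that trainers will use to examine providers' skills related to neonatal resuscitation using stimulation and ventilation equipment". The entry for the BAB OSCEs (Tools 8a-c) likewise begins "Structured checklists that trainers will use to examine". Neither entry restricts trainers to the training day. Section 4b2 places OSCEs at the training day, midline and endline.

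**What else trainers do.** The same simulator-based training goes to all three arms (section 4b1). In the full arm only, "PPCs will be connected to the district trainer via mobile phone for weekly phone calls during the practice periods" (section 4b1, Component 3). Table 1 lists the same contact as "PPC has weekly mobile support from district trainer". Tool 10 in Table 7 logs the "weekly phone support that trainers have with peer practice coordinators (in one study arm only"), using the same word, trainers, as the OSCE entries.

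**Masking.** Section 4b8 says "Randomization or blinding of individual subjects is not feasible in this study because of the district-randomized design". It does not mention assessors. Section 8a says "Observers will be external to the facility", in a passage about observing care at births.

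**Use of the scores.** Section 4b5 lists knowledge and competence as a secondary outcome. For Hypotheses 3 and 4 it says "We will examine differences in competencies and performance at endline between the 3 study groups using generalized linear models", with knowledge and competency scores first among the dependent variables. The listed covariates are provider and facility characteristics. There is no term for the scorer.

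**The concern.** An OSCE score depends on an examiner deciding whether each checklist step was done. If that examiner belongs to the team that delivers the intervention and knows the arm, a small difference in strictness between arms looks the same as a difference in competency. Allocation by district explains why providers cannot be masked. It does not prevent the use of an independent scorer who is not told the arm.

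At stake is the claim that peer-led practice, with or without mobile support, leaves providers more competent at endline than training alone. All four hypotheses name competency, so readers will give this result weight even though it ranks as secondary.

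**Working it through.** **Step 1: Is the trainer a different person from the data collector?** Section 13 lists trainers and data collectors as alternatives, and section 15 has a partner organisation hire and manage the data collectors. These are separate roles, so Table 7's word for the OSCE examiner cannot be read as loose wording for data collectors.

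**Step 2: Is there a safeguard elsewhere?** Section 4b8 covers individual subjects. The section 8a statement concerns birth observers, and being external to a facility is not the same as being independent of the intervention. The documents do not require OSCE scorers to be independent, masked, rotated or checked for agreement.

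**Step 3: Could the analysis separate scorer from arm?** Section 3 selects 6 districts in each of 2 regional groups, splits each six into two sets of three, and draws one district per arm within each set. That gives 2 x 2 = 4 districts per arm. If trainers work by district, which the term district trainer suggests but the plan does not state, each scorer belongs to one arm. Without a scorer term or any crossing of scorers between arms, leniency and treatment effect cannot be told apart.

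**Step 4: Which hypotheses are exposed?**
- Hypothesis 4 (full v. training-only): one arm had weekly contact with trainers, and scorers may know the arm.
- Hypothesis 3 (partial v. training-only): neither arm has trainer phone calls, so only knowledge of the arm can act.
- Hypotheses 1 and 2 (midline v. endline within an arm): constant leniency cancels in the difference. They are exposed only if scorer type or leniency changes between visits.

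**Step 5: How large could it be?** The plan has no figure to reproduce here, so this is an illustration.

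Inputs:
- Table 3 gives a maximum of 651 providers at endline. An even split (assumed) gives 651/3 = 217 per arm. The plan expects actual numbers to be lower.
- Assumed: no true difference; a constant shift b in one arm's scores; SD of 10, 15 or 20 points on a 100-point scale; design effect D of 1 or 5; two-sided 5% test.
- The documents give no SD or intra-class correlation for OSCE scores. With 651/12 = 54.25 providers per district on average, D = 5 corresponds to a district-level correlation of (5 - 1)/(54.25 - 1) = 0.075.

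Formulas: SE = SD x sqrt(2D/217), and false-positive risk = P(Z > 1.96 - b/SE) + P(Z < -1.96 - b/SE).

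Example with SD 15, b = 5:
- D = 1: SE = 15 x 0.0960 = 1.44, b/SE = 3.47, risk 0.94.
- D = 5: SE = 15 x 0.2147 = 3.22, b/SE = 1.55, risk 0.34.

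| Shift | SD | Risk, D = 1 | Risk, D = 5 |
|---|---|---|---|
| 5 points | 10 | 0.999 | 0.64 |
| 5 points | 15 | 0.94 | 0.34 |
| 5 points | 20 | 0.74 | 0.21 |
| 2 points | 10 | 0.55 | 0.15 |
| 2 points | 15 | 0.28 | 0.10 |
| 2 points | 20 | 0.18 | 0.08 |

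Section 4b5 states no clustering adjustment for Hypotheses 3 and 4, which is a separate matter. The D = 1 column is therefore closer to the analysis as described, and the D = 5 column to one that allows for clustering.

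**The case against.** The strongest reply is that Table 7 describes each tool once and does not assign users to visits. Trainers are present on the training day. At the baseline, midline and endline visits, section 7b has data collectors seeking providers' consent. Data collectors may therefore be the intended scorers at those visits. This stands as a possibility, and it is why the plan should settle the point. It is not what Table 7 says, and the plan nowhere assigns OSCE scoring to data collectors.

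Four stronger readings are tempting, and the documents do not support them:
- *The trainer who coaches a facility also scores it.* The plan never says so. The phone contact is a district trainer in Table 1, while section 4b2 also mentions master trainers.
- *Trainers have a stake in the full arm.* They train providers in every arm, so the direction of any leniency is not known from the text.
- *The non-inferiority tests are compromised.* Section 4b2 makes endline the same as midline apart from the qualitative work, and nothing suggests a change of scorer. Setting a 5-point shift between arms beside the 0.06 within-arm margin is not informative.
- *The primary outcomes are affected.* Section 4b5 takes the oxytocin outcome from direct observation of births, and Objective 4 does the same for newborn resuscitation. The multiple-choice knowledge tests leave little room for leniency.

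It is also fair that structured checklists limit an examiner's discretion, that weekly calls end about six months before endline, and that the SD, shift and design effect above are all assumed. These points reduce the likely size of the bias. They do not remove it, because knowledge of the arm outlasts the calls and no safeguard is stated.

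**Conclusion.** The concern holds in a limited form. As written, intervention staff who can know the arm score a secondary outcome that is compared between arms at endline, and the analysis cannot correct for it. Hypothesis 4 is the main exposure, Hypothesis 3 is exposed only through knowledge of the arm, and Hypotheses 1 and 2 only if scoring changes between visits.

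The illustrated risk for 5 points of leniency is 0.74 to 0.999 without clustering and 0.21 to 0.64 with a design effect of 5. For 2 points it is 0.18 to 0.55 and 0.08 to 0.15. All of these exceed 0.05, but they rest on assumed inputs and show what leniency could do, not that it will occur. The plan should be changed because prevention is cheap and later correction is not possible.

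**What to change.** Amend Table 7 and section 4b8 to state that:
- trainers score only the training-day pre- and post-training OSCEs;
- midline and endline OSCEs are scored by the clinician data collectors already at the facility for the 2-3 day visit;
- no one scores in a district where he or she trained or coached;
- scorers are not told the arm;
- the same type of scorer is used at midline and endline.

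If data collectors were always meant to score these visits, the amendment only corrects Table 7 and adds the masking statement.

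The cost is checklist training, which could be added to the one-week data collector workshop in section 7b, and scoring time. Section 8d puts the knowledge and OSCE assessment at 60 minutes, and this could compete with birth observation. Some scorers will infer the arm on site, particularly at midline, where the qualitative sample is stratified by arm and practice level. Where possible, complete OSCE scoring before those interviews. Imperfect masking would remain, but scoring would no longer be done by the staff who deliver the intervention in that district.

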- (a) Pre- and post-training, providers will be assessed on knowledge and OSCE competency tests. There will be separate one-day trainings for BAB & HBB spaced 2 months apart.
- (b) At midline and endline providers will be given BAB and HBB knowledge tests and OSCE skills tests. Facility readiness assessments will also occur at these time points.
- (c) The number of providers in this table is taken from the ACTUAL number of providers that we are aware exist in the Eastern and Western region that attend births. All providers are invited to participate in the intervention and may be assessed.

Direct Clinical Observation: Number of births (women and newborns) to be observed

We specify the sample size of number of births to observe below. The outcome variable is: the percentage of women who **received oxytocin** in correct dose immediately after vaginal birth in three study arms. The hypothesized levels of this variable at each time point are presented below:

Table 4. Hypothesized levels of “percent of women who **received oxytocin** in correct dose “within 1 minute of vaginal birth” in three study arms

Study Arm	Baseline	Midline	Endline
Full	50% (a)	75%	70%
Partial	50%	65%	60%
Training-only	50%	55%	50%

Note:

- (a) A study carried out in 2007 (POPPHI, 2007) found that **20%** of women delivering at health facilities in Uganda received an oxytocin injection between birth and the delivery of the placenta. However, given the small sample size (n=259 births observed) and the fact that the situation may have improved (as it has in many countries), we have conservatively estimated baseline coverage of oxytocin use to be **50%**.

Table 5. Number of **births** to observe (women in labor and delivery)

Study Arm	Baseline	Midline	Endline	Total births
Full Intervention Group (expected: 50% at baseline to 75% at midline to 70% at endline)	189 67 to compare baseline-midline	378 (a) for midline-endline comparison 99, midline-only comparison 67 to compare baseline-midline	378 (a) for midline-endline comparison 189 endline-only (b)	1134
Partial Intervention Group (expected: 50% at baseline to 65% at midline to 60% at endline)	189 to compare baseline-midline	189 , to compare baseline-midline 99, midline-only comparison	189 , endline-only comparison (b)	567
Training-only Group (expected: 50% baseline to 55% at midline to 50% at endline)	189	189 , midline-only comparison	189 , endline-only comparison (b)	567
Grand Total	567	756	756	2079

Notes

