- (a) The number of **378 births** is recommended for each time point in the full package group only. N=378 is based on calculations for midline and at endline is based on a (within-group) non-inferiority calculation in the intervention group. We set the number of health facilities at 54 (9 facilities on average per district * 3 districts * each of 2 regions). This sample size will achieve 80% power to detect a non-inferiority margin difference between the group proportions of providing oxytocin of -0.1000. As shown in the previous table, the percent of deliveries with oxytocin provision at midline (post-intervention) is hypothesized to be 70% in Full group. We assume intra-class correlation (ICC) of 0.005 and significance level of the test is 0.0250.
- (b) The number of **189 births** in each group at endline (only) is based on the following assumptions: This is a two-sample comparison of proportions. We aim to detect a 15% point difference at endline between an intervention group and the training-only group. Training-only group value set at 50%, as this is most conservative. Intervention group value set at 65%. Power is set at 80%. ICC is set at 0.01.
- (c) To avoid oversampling, and to compensate for different caseloads at different facilities, the study team will be given a target number of births to observe and they will stop when they reach this target. There will be no overlap in the number of women observed, because different women will be observed at different time points.

Service Statistic Data Abstraction

There is no sample size calculation for analysis of service delivery statistics because baseline data from the study health facilities are not available.

Qualitative Data: Focus Group Discussions and In-depth Interviews

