16	Semi-structured interview guide: Health care providers	Health care providers will be asked about their experiences with the program and their ideas for how to improve care for postpartum hemorrhage and neonatal asphyxia.
17	Semi-structured interview guide: Stakeholders	Stakeholder will be asked about their opinions about how to strengthen and sustain this program and other efforts to improve care for postpartum hemorrhage and neonatal asphyxia in Uganda.

3) *Number of study contacts* or visits required of participants.

Please see table 2 on page 5 for details. Briefly, women in labor, key stakeholders and facility in-charges will each have a maximum of only one study contact. Providers could have up to 12 study contacts, if they were selected for all types of data collection, but this will be rare. Similarly, peer practice coordinators could have up to 12 study contacts plus regular telephone contact with a member of the research team.

4) **Expected duration of the study.**

After JHSPH IRB and Ugandan IRB are obtained, the study will take 18 months.

5) A brief **data analysis plan** and description of the **nature of the variables** to be derived.

Primary Outcome:

- For the postpartum hemorrhage component, the primary outcome will be the proportion of women who received **oxytocin** (at correct dosage) within one minute of a vaginal birth, before delivery of the placenta. Data for this outcome will be obtained from the direct clinical observations.
- For the neonatal asphyxia component, the primary outcome will be the proportion of babies not breathing at birth who are breathing or being ventilated by one minute.

Secondary Outcomes:

- Change in providers' knowledge and competence related to postpartum hemorrhage and neonatal resuscitation, as assessed by knowledge tests and observed performance with a simulator.
- Trends in PPH and neonatal asphyxia/mortality rates, by abstracting *aggregated* monthly service statistics from each facility.
- Identification of structural, environmental and behavior factors that are associated with routine, frequent practice with the simulator.

Data will be entered using [name]/Foxpro/SPSS/CsPro and analyzed using Stata 12.

Quantitative data analysis

Specific Hypotheses:

In BAB and in HBB related to the primary outcomes (see Section 4b5):

1. Provider competencies and performance will not decline (i.e. will be non-inferior) between midline and endline in the *full* package group.

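### No planned model names the declared newborn (HBB) primary outcome, and the oxytocin non-inferiority test that sized the full arm has no rule in Section 4b5

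*Combined protocol and SAP*

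**What the plan says.** Section 4b5 declares one primary outcome per component. For haemorrhage it is correctly dosed oxytocin within a minute of vaginal birth. For newborns: "For the neonatal asphyxia component, the primary outcome will be the proportion of babies not breathing at birth who are breathing or being ventilated" (within one minute). Hypotheses 1 to 4 are introduced with "In BAB and in HBB related to the primary outcomes (see Section 4b5", and each covers both competency and performance.

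The analysis text then specifies:

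- **Hypotheses 1 and 2 (midline to endline, full and partial arms).** "Two-sided 90% confidence intervals (CI) for the difference in average knowledge and competence scores between midline and endline will be constructed". The upper bound is compared with "the pre-specified non-inferiority margin of 0.06", and the claim is made at the 0.05 level. The models take knowledge and competencies as dependent variables.
- **Hypotheses 3 and 4 (arms compared at endline).** There are four listed dependent variables: the scores, oxytocin, placenta inspection, and "proportion of newborn checked for breathing within 1 minute".
- **Additional analyses.** These cover service delivery statistics, practice logs and aggregated register data.

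The sample size section (3c, Table 5 note (a)) justifies 378 full-arm births at midline and again at endline by a within-arm oxytocin comparison: "This sample size will achieve 80% power to detect a non-inferiority margin difference between the group proportions of providing oxytocin of -0.1000". It adds that the "significance level of the test is 0.0250", with an ICC of 0.005 and 54 facilities.

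**The concern.** The declared outcomes and the specified analyses do not line up in two places.

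First, the newborn primary is Objective 4c, whose denominator is babies not breathing at birth. The newborn item in the Hypotheses 3 and 4 list is Objective 3c, whose denominator is all newborns and whose numerator is being checked. A provider could check every baby promptly and still fail to ventilate the few who need it, so one outcome cannot stand in for the other. Followed as written, the plan names no arm comparison and no midline-to-endline estimate for one of its two primary outcomes. Adding either after the data are in would be post hoc.

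Second, the only non-inferiority rule in 4b5 is written for scores. The rule that sized the full arm concerns a different outcome, with a different margin and level. An analyst testing oxytocin would have to choose between the two, possibly after seeing the result.

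**Working it through.** **Is the newborn primary named in any model?**

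| Place in 4b5 | Dependent variable | Newborn primary named? |
|---|---|---|
| Hypotheses 1–2 | knowledge and competence scores | No |
| Hypotheses 3–4 | scores; oxytocin; placenta inspection; checked for breathing | No |
| Additional 1 | service delivery statistics, not itemised | No |
| Additional 2 | practice log counts | No |
| Additional 3 | register services and health outcomes | No |

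**Reproducing the 378.** Inputs from Table 5 note (a): 70% at both time points, margin 0.10, level 0.025, power 80%, ICC 0.005, 54 facilities.

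- Before clustering: n = (1.96 + 0.8416)² × (0.70×0.30 + 0.70×0.30) / 0.10² = 330 per time point.
- With 7 births per facility, the design effect is 1 + 6 × 0.005 = 1.03, giving 340.
- In whole births per facility, 6 × 54 = 324 is too few and 7 × 54 = 378 is enough. The 378 is reproduced.

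This confirms that the sized test is a one-sided 0.025 test on the oxytocin proportion. The table row itself reads "expected: 50% at baseline to 75% at midline to 70% at endline", whereas the note calls 70% the midline level. I use 70% because it reproduces 378; a constant 75% would give 6 × 54 = 324.

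**Does the choice of rule matter?** Power = Φ(margin/SE − z), with no true change from 70% and SE = √(0.42/378) = 0.0333.

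- Sizing rule (0.10, z = 1.96): Φ(3.00 − 1.96) = Φ(1.04) ≈ 85% (84% with design effect 1.03).
- Score rule applied to oxytocin (0.06, z = 1.645): Φ(1.80 − 1.645) = Φ(0.155) ≈ 56% (55% with design effect 1.03).

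**Which births depend on the missing test?** The full arm has 378 − 189 = 189 extra births at midline and 189 extra at endline. The endline extras also enter the Hypothesis 4 comparison. The midline extras have no other specified use in Hypotheses 1 to 4: 189/2,079 = 9% of the stated total.

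**Newborn denominator.** The documents give no rate of babies not breathing at birth, so I assume 3% to 15%. I also assume direct clinical observation is the source. The 95% half-width for a difference near 50% is 1.96 × √(0.25/n₁ + 0.25/n₂), before clustering. The normal approximation is rough at the smallest counts.

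| Assumed rate | Babies per 189 | Babies per 378 | All 756 endline births | Half-width, partial v training-only | Half-width, full v training-only |
|---|---|---|---|---|---|
| 3% | 5.7 | 11.3 | 22.7 | ±58 points | ±50 points |
| 5% | 9.5 | 18.9 | 37.8 | ±45 | ±39 |
| 10% | 18.9 | 37.8 | 75.6 | ±32 | ±28 |
| 15% | 28.4 | 56.7 | 113.4 | ±26 | ±23 |

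**The case against.** The strongest defence is that the newborn primary could reach analysis through the registers. Table 2 gives register abstraction as the source for objectives 4 and 5, the supplemental register in Table 7 records bag-and-mask resuscitation, and the service-statistics model has arm-by-time terms. Section 4b5 names direct observation as the source for oxytocin but names none for the newborn outcome. Part of this stands: the source needs confirming, and the 6 to 28 count holds only under direct observation. It does not close the gap. Objective 4 is framed as measured during observed care, the service-statistics model does not itemise its outcomes, and nothing shows that the registers record status at one minute.

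It can also be said that 4b5 does cover performance, because Hypotheses 1 and 2 state that it will be non-inferior. That is right about intent. What is absent is a performance variable, model, margin and level.

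Nor does the brevity of the plan explain the gap. It specifies models for placenta inspection, which is not a primary outcome, and for practice logs.

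A reader might infer that all 378 extra full-arm births (2 × 189, or 18% of 2,079) serve no specified analysis. The documents do not support that, since the endline half is used in Hypothesis 4. A reader might also infer that so few babies per arm rule out any covariates. The Hypotheses 3 and 4 model pools the three arms, so the relevant count is about 23 to 113 babies. That is thin at the low end but not prohibitive throughout the range.

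**Conclusion.** The point holds and should be corrected before the data are analysed. One of two declared primary outcomes is named in no planned model, and a different newborn outcome occupies its place in the list for Hypotheses 3 and 4. The oxytocin non-inferiority test that justifies 378 full-arm births per time point has no model, margin or level in 4b5. The one rule given there would cut its power from about 85% to about 56% if carried over, assuming no true change from 70%. These omissions rest on the text alone. Only the newborn counts and interval widths depend on the assumed 3% to 15% and on direct observation as the source.

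Three stronger readings go too far:

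- The plan does not ignore these babies altogether. The checked-for-breathing outcome includes them among all newborns, and HBB skill scores are modelled.
- Oxytocin is not left unanalysed. It is in the Hypotheses 3 and 4 list; only its midline-to-endline test is missing.
- The 0.10 margin cannot be read across to the partial arm, because the note confines that calculation to the full package group.

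Power under the declines hypothesised in Table 4 is a separate sample-size question and does not bear on this point.

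**What to change.** 1. **Hypotheses 3 and 4.** Add the newborn primary as a dependent variable, with babies not breathing at birth as the denominator, and label checked-for-breathing as secondary. Confirm direct clinical observation as the source, and confirm that the observation form times status at one minute (the form is not in the documents). Report counts and a risk difference with an interval that allows for clustering, by facility at least, bearing in mind that districts are the unit of assignment. Make the unadjusted estimate the main one and limit covariates to what the pooled endline count supports.
2. **Hypotheses 1 and 2.** Under Hypothesis 1, add the full-arm endline-minus-midline oxytocin difference with a cluster-robust two-sided 95% interval. Declare non-inferiority if the lower bound lies above −0.10, which is the margin and level of Table 5 note (a). State that the 0.06 margin, 90% interval and 0.05 level apply to scores only. The documents set no margin for oxytocin in the partial arm or for the newborn primary in either arm. There, report the midline-to-endline estimate with a clustered interval unless the team states a margin in advance.
3. **Expectations.** State beforehand the expected newborn denominator and interval width, and that a non-significant result will not be read as no effect.

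The cost is analysis-plan wording and a check of the form; no births are added. The downside is that the newborn intervals will be visibly wide, and clustering will widen them further.
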